2.6.4 Glucocorticoids

The striking entry of steroids into management of RA more than 60 years ago was followed by uncertainty about their value. Short-term glucocorticoids reduce synovitis. In the long term they decrease joint damage (Kirwan et al., 2007) but incur substantial adverse risks, such as infections and osteoporosis, and their overall risk/benefit ratio is deemed unfavourable. Glucocorticoids can be especially useful in two settings. First, short-term use during flare-ups in disease can lead to rapid improvement and allow other treatments, such as DMARDs, which have a slower onset of action to be adjusted. Use of steroids in this way is low risk. Oral or intramuscular glucocorticoids are administered by many centres in this setting. Second, intra-articular glucocorticoids are a highly effective local treatment for individual active joints (Goossens et al., 2000).

2.6.5 Supportive Treatments

Effective non-drug treatments span exercise, joint protection, foot care, and psychological support (Hurkmans et al., 2009). Patients' education is also of crucial importance. All these strategies are best delivered by a multidisciplinary team of rheumatologists, nurses, therapists, and podiatrists.

Management of comorbidities is important; they reflect both the disease process and its treatment. Comorbidities include cardiac disease, bone disease, and depression. Conventional guidance recommends annual reviews to detect and treat comorbidities. Systemic complications such as Sjögren's syndrome, lung disease, and vasculitis, need specific treatments, which range from eye drops to cytotoxic drugs. Surgical treatment, particularly joint replacement surgery, is vital to maintain function when joints fail, and collaboration with orthopaedic specialists is required.

2.7 Complications

2.7.1 Death and comorbidities

Patients with RA continue to have increased risks of mortality, mostly from cardiovascular disease and infection. The major causes of mortality mirror rises in specific comorbid disorders. Risks of both myocardial infarctions and strokes are amplified in individuals with RA (Lévy et al., 2008). Although this increase could indicate inflammation-associated vascular damage, identification and treatment of cardiovascular risk factors is important; some evidence shows that methotrexate reduces cardiovascular risks in patients with RA. Comorbid disorders are associated with increased disability and frequent medical consultations (Michaud and Wolfe 2007).

A slightly elevated risk of lymphoma and lymphoproliferative malignant disease is associated with RA activity (Kaiser, 2008). Prevalence of lung cancer is also raised, potentially due to increased cigarette smoking in patients with RA (Khurana et al., 2008).

2.7.2 Treatment-associated comorbidities

Treatment-associated comorbid disorders include osteoporosis and cataract (steroids), gastrointestinal ulceration (NSAIDs), and infections and melanoma (biological agents and steroids). Many of these associations are confounded by RA activity (Nyhall-Wahlin, 2009).

2.8 Dietary Pattern and Rheumatoid Arthritis

The most common dietary patterns or diets that have been used to treat RA include: Mediterranean-style and vegetarian diets, ‘elemental’ eating plans and ‘elimination’ diets combined with a period of fasting. Studies have looked at the effects of vegetarian diets on RA such as vegan diets or lacto-ovo-vegetarian (which include dairy products and eggs) diets.

A Mediterranean-style eating pattern is typically high in fruit, vegetables, cereals (traditionally unrefined) and legumes, and contains moderate amounts of red meat and high amounts of fish and olive oil (Trichopoulou et al. 2005). Skoldstam et al. (2003) suggested that this dietary pattern may be beneficial to health because of the relatively high level of antioxidants and unsaturated fatty acids. Hagfors and colleagues (2002) investigated the efficacy of a Mediterranean diet (MD) compared to ordinary western diet for suppression of disease activity in patients with RA. 26 RA patients received MD diet throughout the three weeks of the Outpatient based rehabilitation programme (ORP). Then, for the next nine weeks all patients returned home and back with their everyday life are instructed to continue with the MD diet prepared by themselves. MD group need to follow Cretan Mediterranean diet were they are allowed to used olive oil and canola oil in food preparation, baking and in salad dressing. They were instructed to reduce the amount of yogurt, cheese, milk or choose low fat products and were encouraged to drink green or black tea. Whereas, another 25 patients were in control group needs to continue with their regular diet. Study showed decrease in DAS 28 score ($p<0.001$), decrease in HAQ ($p=0.020$) and in SF-36 Health Survey; increase in vitality ($p=0.018$) and decrease in “compared with one year earlier ($p=0.016$) in MD group. No significant changes seen in control group at the end of study.

The same authors investigated the effect of Mediterranean diet on the antioxidant intake, plasma antioxidant and oxidative stress status of the patients with RA (Hagfors et al., 2003). Cretan Mediterranean diet, which contain large amount of fruit, vegetables, pulses, cereal, fish, nut, high omega 3 fatty acid, high content of α -linolenic acid and moderate and regular alcohol consumption especially red wine. Significantly higher intake of vitamin C ($p=0.014$), vitamin E ($p=0.007$) and selenium ($p=0.004$) and lower intake of retinol ($p=0.049$) has been reported in the MD group, as compared to the CD group. There is no changes in urine MDA or in the plasma level of antioxidants, from baseline to the end of the study. The levels of retinol, vitamin C and uric acid were negatively correlated to disease activity variables. No correlation found between antioxidant intake and the plasma level of antioxidants in RA patients.

The efficacy of a dietary plant-derived polysaccharide supplement in patient with RA has been evaluated by Alavi et al. (2011). 33 RA patient received powder AC contained Ambrotose Complex, a dietary supplement approved as source of dietary fiber, taken 1.3g/day orally. The main active ingredient of AC contains aloe vera gel extract, arabinogalactan, gum ghatti, gum tragacanth and glucosamine. Whereas, another 33 RA patients in a placebo group received rice flour powder with identical texture and appearance as AC supplement. All patient consumed supplementation for 8 weeks. Study findings showed there is no significant overall effect on patient outcomes in AC group. AC supplementation resulted in 12% reduction in serum-N- glycosylation (GoF) ($p=0.035$) whereas the placebo group did not result in any significant changes. There was a decrease in DAS score in AC group compared to placebo group ($p=0.009$).

RCTs or clinical controlled trials that compared different diets with an ordinary/ usual diet and assessed the impact on a range of primary outcomes, e.g. pain, functional status (i.e. the capacity to perform everyday tasks), joint stiffness and fatigue, as well as any possible adverse effects (such as the number of withdrawals because of adverse events and unwanted weight loss) were included. Overall, changing from a diet that is 'less healthy' (e.g. high in saturated fatty acids) to a 'healthier' diet may explain some of the positive changes in RA symptoms observed with different dietary patterns. In summary, studies investigating the role of different dietary patterns in the treatment of RA have reported improvement in a number of symptoms, but the potential mechanisms of action are still unclear.

There is limited number of human clinical trial involving RA patients and dietary fiber intake. Thus, this study findings will help to figure the effect of high fiber consumption among RA patient on their disease severity, blood inflammatory molecules, antioxidant level, oxidative stress and nutritional status changes.

2.8.1 Fiber intake and inflammatory process

Dietary changes have been proposed to be linked to improvements in RA through a number of mechanisms, such as a decrease in the inflammatory process associated with the condition, an increase in antioxidant levels, altered lipid profiles and/or possible changes in gut microbiota composition (Hagen et al. 2009). However, the mechanisms underlying the pathogenesis of joint diseases are for the most part unknown. It has, nevertheless, been demonstrated that diet and lifestyle can play a role in their pathogenesis as well as improve the course of RA. Rich in complex carbohydrates, fiber is able to promote saccharolitic microbiota favouring short-chain

fatty acid production. These metabolites have been shown to possess positive immune-modulating activity by modifying the cytokine production profile of TH cells, promoting intestinal epithelial barrier integrity, resolving intestinal inflammation, and regulating the acetylation of lysine residues, a covalent modification that affects proteins involved in a variety of signalling and metabolic processes (Hagen, 2009).

Inappropriate dietary intake are related to the insufficient intake of carbohydrate dietary fiber may severe RA symptoms by triggered the cytokines production. The immune cell produce large production of immune mediator such as tumor necrosis factor-alpha (TNF- α), interleukin 1 (IL-1), interleukin 6 (IL-6) and T-cells. The volume of synovial fluid increase the narrow joint space causing inflamed tendon, thinning of cartilage, swelling, bone erosion and impaired mobility. Thus, increasing dietary fiber intake from fruits, vegetables and wholegrain may help to alleviated RA symptoms by reduce inflammation.

Dietary fiber is a carbohydrate polymers which neither digested or nor absorbed in human intestine are subjected to bacterial fermentation in gastrointestinal tract which affect the gastrointestinal balance and changes. This include composition of bacterial, microbial metabolic activities that include the production of fermentative end-products. Diet rich in fiber ($> 30\text{g/day}$) seen to have shifts in bacterial diversity and production of microbial derived fecal fermentative as end products within 24 hours in humans study that switch meat based diet to diet rich in fiber (David et al., 2013).

Human enzymes only capable to degrading few glycosidic linkages present in a subset of carbohydrates including starch polysaccharide via the action of pancreatic and salivary amylase, and disaccharides sucrose and lactose via the brush border disaccharides, sucrose and lactase (Cantarel et al., 2012). However carbohydrate that escaped digestion by human enzymes are substrate for bacterial fermentation within the gastrointestinal tract. The major bacterial fermentative end product of complex carbohydrate are short chain fatty acid (SCFA_s) (Hannah, 2017). It is notable also as acetate, propionate and butyrate (Cummings et al., 1987). SCFA_s is an important indicator for bacterial fermentation in colon. SCFA_s may influence gastrointestinal epithelial cell integrity, glucose homeostasis, lipid metabolism, appetite regulation and immune function (Koh et al., 2016).

Butyrate is the primary energy source for colonocytes and protect again cancer and inflammation by inhibiting histone deacetylases (HDACs) (Flint et al., 2012). HDACs inhibitor reported used for cancer therapy due to its function as anti-inflammatory or immune suppression (Johnstone, 2002). Butyrate suppresses proinflammatory effector in lamina propria macrophages (Chang et al., 2014) and differentiation of dendritic cells from bone marrow stem

cells (Singh et al., 2010) via HDAC inhibition. Thus, immune system become hyporesponsive to the beneficial of the bacterial. SCFA help to regulate cytokine expression in T cells and generate T cell regulation thorough HDCs inhibition. Effector T cells then enhanced glycolysis process and inhibition of glycolysis promotes cell generation (Shi et al., 2011). This help in induces tolerogenic and anti-inflammatory profile of T cell and reduce inflammation.

Another study showed that gum Arabic has immune modulator effect on RA. Gum Arabic fermentation by colonic bacteria increases serum butyrate concentrations. Result significantly showed significant decrease in level of serum TNF α (p value 0.05), ESR (p value 0.011) and number of swollen and tender joints in RA patients significant decrease in disease severity score DAS 28 (p value 0.001) after 12 week consumption (Ebtihal et al., 2018). Thus, the bacteria release does help reduce the inflammation that are the main trigger for symptoms of RA.

3.0 OBJECTIVES

General Objective

- To determine the effectiveness of high fiber multigrain supplementation among the rheumatoid arthritis patients

Specific objectives:

In the current study we would like to test the hypothesis that high fiber multigrain supplementation among the rheumatoid arthritis patients would:

- (a) improve the level of clinical disease severity measures
- (b) improve the blood inflammatory molecules and antioxidative status
- (c) improve the overall nutritional status

4.0 RESEARCH DESIGN

This is a single center, with balanced randomisation [1:1], parallel group, open labelled study. The allocation ratio is 1:1.

5.0 SAMPLE SIZE ESTIMATION

The results from the previous study (Jalili et al. 2014) among RA patients will be used to determine the trial sample size. The following formula will be used to calculate the sample size for each arm:

$$n = \frac{2x[z_{(1-\alpha/2)} + z_{(1-\beta/2)}]^2}{\Delta^2}$$

Thus, for this study,

n = 21 subjects

Where n = sample size,

Z = 0.8416 (80% power; 95% confidence interval)

Z = 1.96

= mean difference/standard deviation

With consideration that the dropout rate is 20%, thus the sample size would be $21 + 4 = 25$ participants for each arm.

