8.0 VULNERABILITY OF THE SUBJECT/PARTICIPANT

The principle investigator and co-investigators will comply with the applicable regulatory requirement(s) related to the reporting of unexpected serious adverse drug reactions to the

regulatory authorities and the institutional review board. Any complaints (particularly gastrointestinal discomfort) from the subject will be recorded, and they will be arranged to receive immediate medical care at HUSM. If the complaints persist during supplementation period, the subject will be stopped by the investigator from the trial. The affected subject will be followed up tightly.

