To generate a random allocation sequence, a computer-generated list of random numbers will be used. Simple randomization, where a 1:1 allocation ratio (1 supplement group: 1 control group) will be applied.

Step 2: Concealment of this sequence from the investigators enrolling participants

The allocation sequence will be concealed from the investigator enrolling and assessing participants in sequentially numbered, opaque, sealed and stapled envelopes. To prevent subversion of the allocation sequence, the name and date of birth of the participant will be written on the envelope.

Step 3: Implementation

Determination of whether a patient would be supplemented by multigrain powder (S) or control (C) will be made by reference to a statistical series based on random sampling numbers drawn up by statistician; the details of the series are unknown to any of the investigators or to the coordinator. After acceptance of a patient by the panel, the appropriate numbered envelope will

be opened at the clinical trial ward; the number indications inside will be notified if the patient will to be S or a C group, and this information will be then given to the medical officer in charge of the trial.

(ii) Matching

Not applicable.

(iii) Blinding

Participants will be notified whether they have been randomly assigned into either the S or C group since this is an open-labelled trial. However, only data collectors, coordinator and medical officer in charge of the trial are aware of the allocated arm. Investigators, data analyst and outcome adjudicator will be kept blinded to the allocation.

(c) Study Outcomes

The patient outcome measures will be assessed at two time points: baseline and end of treatment period (week-12).

(i) Primary clinical outcomes

The primary efficacy criterion is clinical remission as assessed by changes in the DAS-28 score from baseline (Day 0) to end of treatment (week-12).

1. Disease Severity Score (DAS-28)

Assessment of number of tender (t28) and swollen (s28) joints out of 28 (10 proximal interphalangeal, 10 metacarpophalangeal, 2 wrists, 2 elbows, 2 shoulders and 2 knees) will be conducted by a rheumatologist and the validated DAS-28 form will be filled to calculate disease activity index according to the following formula:

$$\text{DAS-28} = 0.56 \sqrt{t28} + 0.28 \sqrt{s28} + 0.70 \ln(\text{ESR}) + 0.014 \text{ VAS} \quad (\text{Harrison et al., 2008})$$

Where ESR = erythrocyte sedimentation rate

 VAS = Visual Analogue Scale

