20.0 WITHDRAWAL CRITERIA

The investigator may terminate participation in the study if:

- (a) The participant will be terminated if they meet an exclusion criterion (either newly developed or not previously recognized) that precludes further study participation.
- (b) Any clinical adverse event (AE), serious adverse events (SAEs), laboratory abnormality, or other medical condition or situation occurs such that continued participation in the study would not be in the best interest of the participant.
- (c) The participant will be terminated if they take any probiotic during the study time. However, the use of antibiotic is allowed if it is needed.

All withdrawals and dropouts of enrolled subjects from the trial will be reported and explained on the CRFs. Any terminated/withdrawal will be follow up if possible.

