21.0 PROPOSED DATA ANALYSIS

Data analysis, in the form of intention-to-treat will be performed at the end of the study. All statistical analyses will be implemented using version 24.0 of the Statistical Package for Social Sciences (SPSS Inc., Chicago, IL) software. An alpha level of 0.05 will be used for all statistical tests. The following statistical methods has been proposed:

- (a) For descriptive statistics, categorical and continuous data will be presented as percentages, means with standard deviations, median and range.
- (b) For inferential tests $p < 0.05$ will be used to indicate for statistical significance (Type I error) (two-tailed).
- (c) Assumptions will be checked for normality tests, and transformation will be applied as corrective procedures.
- (d) Analysis of the primary, secondary and tertiary outcomes will be measured using Pearson's correlation, multiple regression, repeated measures mixed models, logistic regression, and analysis of covariance.

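### Minor correction: 25 per arm covers 16% dropout, not the stated 20%; at 20% an expected 20 per arm are evaluable, one short of the plan's own 21

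*Combined protocol and SAP*

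**What the plan says.** Section 5.0 arrives at 21 subjects per arm from a two-group formula for means, with 1.96 for the significance level and "Z = 0.8416 (80% power; 95% confidence interval" for power. The effect enters as a standardised difference, "mean difference/standard deviation", but its value is not visible in the available text. The section then adds the allowance: "With consideration that the dropout rate is 20%, thus the sample size would be $21 + 4 = 25$ participants for each arm".

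Three other places bear on what a dropout means for the analysis:

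- Section 14.0, under Study Outcomes, fixes the assessment times: "The patient outcome measures will be assessed at two time points: baseline and end of treatment period (week-12".
- Follow-up after stopping is intended. Section 8.0 says of a subject stopped for persistent complaints: "The affected subject will be followed up tightly". Section 20.0 is less firm: "Any terminated/withdrawal will be follow up if possible".
- Section 21.0 names the analysis principle: "Data analysis, in the form of intention-to-treat will be performed at the end of the study". It gives no rule for a missing week-12 value.

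**The concern.** A dropout rate describes the share of enrolled patients who are lost. To keep a required number after losses, that number is divided by the share retained. Section 5.0 instead takes its percentage of the smaller, required number and adds it on, then rounds the fraction down. Both steps push the enrolled number the same way, too low.

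What is at stake is whether the sample-size paragraph is true. It tells an ethics committee or a reader that 25 per arm absorbs 20% dropout and still leaves the 21 needed for 80% power. By its own figures it does not. The consequence for the trial is modest: one expected evaluable patient per arm.

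**Working it through.** **Inputs.** Required per arm 21, dropout 20%, enrolled per arm 25, z-values 1.96 and 0.8416 (all section 5.0); two-sided 5% level (section 21.0); 1:1 allocation (section 4.0). The standardised difference, Delta, is not visible and is treated as a range below.

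**Reproducing the plan's 25.** 21 x 0.20 = 4.2, taken as 4; 21 + 4 = 25. The figure is reproduced by a percentage of the required number, rounded down.

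**What 25 delivers.**

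- Expected evaluable at 20% dropout: 25 x 0.80 = 20.
- Largest dropout that still leaves 21: (25 - 21)/25 = 4/25 = 16%.
- Rounding the plan's own sum up does not repair it: 21 x 1.20 = 25.2, so 26, and 26 x 0.80 = 20.8.
- Dividing by the share retained: 21/0.80 = 26.25, so 27 per arm (54 in total, against 50), and 27 x 0.80 = 21.6.

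None of these counts uses Delta.

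**Which Deltas are compatible with 21.** The plan's formula with its own z-values is n = 2(1.96 + 0.8416)²/Delta² = 15.698/Delta². If the result was rounded up, the unrounded n was above 20 and at most 21. If it was rounded to the nearest whole number, n was from 20.5 to below 21.5. Together they span n above 20 and below 21.5, so Delta runs from about 0.855 to just under 0.886. The limits themselves fall outside: Delta = 0.886 gives n = 19.997, which rounds up to 20, and Delta = 0.854 gives n = 21.52, which rounds to 22.

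**Power at 20 and at 21 per arm.** Normal approximation, unadjusted two-group comparison: power = Phi(Delta x √(m/2) - 1.96), with m evaluable per arm.

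| Unrounded n | Delta | Power, m = 20 | Power, m = 21 | Loss (points) |
|---|---|---|---|---|
| 20 (limit, not attained) | 0.8859 | 80.0% | 81.9% | 1.9 |
| 20.5 | 0.8751 | 79.0% | 80.9% | 1.9 |
| 21 | 0.8646 | 78.1% | 80.0% | 1.9 |
| 21.5 (limit, not attained) | 0.8545 | 77.1% | 79.1% | 2.0 |

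In the first row power at 20 per arm reaches 80% only at n = 20 exactly, and there the formula would have returned 20 rather than 21.

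**The case against.** **Intention-to-treat keeps all 25.** It keeps all 25 in the analysis set, but it does not create an outcome. The only post-baseline assessment is at week 12, so a patient lost before then has no post-baseline DAS-28. Adding a dropout allowance at all makes sense only if dropouts reduce the number who contribute.

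**Stopping the supplement is not the same as being lost.** This stands. Sections 8.0 and 20.0 plan follow-up of stopped patients, so some will have week-12 data. If the sponsor expects true loss to be below 20%, section 5.0 should give that rate.

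**Adding a percentage of the required number is a common shortcut, and the section does not say what the 20% is a fraction of.** True, but the ordinary meaning of a dropout rate is a share of those enrolled, and even the shortcut was rounded down.

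**The effect is within the design's own noise.** Largely so. Randomisation is simple, without blocks (sections 11.0 and 14.0). With 50 patients the arm size has a standard deviation of √(50 x 0.25) = 3.5, and an exact 25:25 split has a probability of about 11%. The 20 evaluable is therefore an expected value, not a certainty.

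**The power figures are not the trial's power.** Also fair. Section 21.0 lists analysis of covariance and mixed models among its methods. As an illustration only, if the formula's standard deviation is that of the week-12 score and its correlation with baseline were 0.3 or 0.5, then 20 per arm would be worth 20/(1 - 0.09) = 22 or 20/(1 - 0.25) = 27 in an unadjusted comparison. The documents give no correlation and assign no method to DAS-28, so this gain cannot be counted on.

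These points limit how much the error matters. They do not make 25 the number that leaves 21 after 20% dropout.

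Two stronger readings should be resisted. A reader might infer that the trial is materially underpowered; a loss of about 2 points under the plan's own formula does not support that. A reader might also infer the opposite, that 80% could still be met at 20 per arm if Delta is near the top of the range. It cannot under the plan's formula with rounding up: any Delta for which the formula needs more than 20 gives less than 80% at 20.

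**Conclusion.** The dropout allowance in section 5.0 is wrong as written, and the correction is minor. At the stated rate, 25 per arm leaves an expected 20 evaluable instead of 21 (40 instead of 42 in total), and the allowance covers 16%.

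These counts rest only on figures printed in section 5.0 and on reading the dropout rate as a share of those enrolled, with evaluable meaning a patient who has week-12 data. The power statement (about 77.1% to just under 80% at 20 per arm, roughly 2 points below 21 per arm) rests further on the unseen Delta lying in the range that returns 21, on the normal approximation, and on an unadjusted comparison. Whether 21 is itself the right requirement cannot be checked from the available text.

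**What to change.** Keep 25 per arm and restate the last sentence of section 5.0 along these lines: 25 per arm allows for 16% dropout (21 evaluable); at 20% dropout an expected 20 per arm are evaluable, with power of [value recomputed by the sponsor from its actual Delta]. This costs one sentence and one power figure, with no change to design or recruitment.

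For reference, if the sponsor prefers to keep 21 evaluable at 20% dropout, the matching number is 27 per arm, which is four more patients in total.
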